11.3 Methods for Evaluation of Measurable Disease

All measurements should be taken and recorded in metric notation, using a ruler, calipers, or digital measurement tool. All baseline evaluations should be performed as closely as possible to the beginning of treatment and never more than 14 days from the date of registration.

The same method of assessment and the same technique should be used to characterize each identified and reported lesion at baseline and during follow-up.

11.4 Evaluation of Best Response

The best overall response is the best response recorded from the start of the treatment until disease progression (taking as reference for progressive disease the smallest measurements recorded since the treatment started). If a response recorded at one scheduled MRI does not persist at the next regular scheduled MRI, the response will still be recorded based on the prior scan, but will be designated as a non-sustained response. If the response is sustained, i.e. still present on the subsequent MRI, it will be recorded as a sustained response, lasting until the time of tumor progression. Participants without measurable disease may only achieve SD or PD as their best "response."

11.5 Other Effect Measures

Neurological Exam

Although not used for determining response, it is useful to evaluate changes in the neurological exam compared to the previous exam. The following scale may be used:

- +2 Definitely better
- +1 Possibly better
- 0 Unchanged
- 1 Possibly worse
- 2 Definitely worse

Performance Status:

Participants will be graded according to KPS score

Overall survival time:

From date of first dose (date of first post surgery treatment for participants in Cohort 1) to date of death due to any cause.

Progression-free survival time:

From date of first dose (date of first post surgery treatment for participants in Cohort 1) to date of progression or death. Participants who stop treatment for causes other than progression may be censored if other therapy is initiated or if regular assessments for assessing progression are no longer available.

11.6 Response Review at DFCI Coordinating Center

Central review of MRI or CT scans is planned for participants who achieve CR, PR, or PFS6.

Central review will be performed by [name] or her designee for registered subjects who have been determined by the enrolling institution as having achieved PFS6, complete radiographic response, or partial radiographic response. When a participant's films are requested by the DFCI Coordinating Center and Overall PI, all films of all views from pre-registration and subsequent scans must be submitted for central review. Once the Central Review is complete, the central review results can be made available to the local PI.

When imaging studies are requested by the Coordinating Center:

- All films of all views from pre-registration and subsequent scans must be submitted for central review.
- Transfer images to compact disc, labeled with study/case number and deidentified per institution's local policy.
- A copy of all scan reports must be attached for inclusion in the submission.
- A memo detailing what is being submitted should be included with submission (a template memo will be provided by the DFCI Coordinating Center)
- Ship to:

[name] [name] c/o [name] Center for Neuro-Oncology Dana-Farber Cancer Institute [name] [contact]

The submitting institution is responsible for the costs of shipping and handling.

12. DATA REPORTING / REGULATORY REQUIREMENTS

Adverse event lists, guidelines, and instructions for AE reporting can be found in Section 7.0 (Adverse Events: List and Reporting Requirements).

12.1 Data Reporting

12.1.1 Method

The ODQ will collect, manage, and perform quality checks on the data for this study.

12.1.2 Responsibility for Data Submission

Investigative sites within DF/HCC or DF/PCC are responsible for submitting data and/or data forms to the ODQ according to the schedule set by the ODQ.

Form	Submission Timeline		
Eligibility Checklist	Complete prior to registration with ODQ		
On Study Form	Within 30 days of registration		
Baseline Assessment Form	Within 30 days of registration		
Treatment Form	Within 14 days of treatment administration		
Adverse Event Report Form	Within 14 days of AE assessment/notification		
Response Assessment Form	Within 14 days of the response assessment		
Off Treatment/Off Study Form	Within 14 days of completing treatment or being taken off study for any reason		
Follow up/Survival Form	Within 14 days of the protocol defined follow up visit date or call		

12.2 Data Safety Monitoring

The DF/HCC Data and Safety Monitoring Committee (DSMC) will review and monitor toxicity and accrual data from this study. The committee is composed of clinical specialists with experience in oncology and who have no direct relationship with the study. Information that raises any questions about participant safety will be addressed with the Overall PI and study team.

The DSMC will review each protocol up to four times a year or more often if required to review toxicity and accrual data. Information to be provided to the committee may include: up-to-date participant accrual; current dose level information; DLT information; all grade 2 or higher unexpected adverse events that have been reported; summary of all deaths occurring with 30

days of intervention for Phase I or II protocols; for gene therapy protocols, summary of all deaths while being treated and during active follow-up; any response information; audit results, and a summary provided by the study team. Other information (e.g. scans, laboratory values) will be provided upon request.

12.3 Multicenter Guidelines

This protocol will adhere to the policies and requirements of the DF/HCC Multi-Center Data and Safety Monitoring Plan. The specific responsibilities of the Overall PI, Coordinating Center, and Participating Institutions and the procedures for auditing are presented in Appendix B.

- The Overall PI/Coordinating Center is responsible for distributing all IND Action Letters or Safety Reports to all participating institutions for submission to their individual IRBs for action as required.
- Mechanisms will be in place to ensure quality assurance, protocol compliance, and adverse event reporting at each site.
- Except in very unusual circumstances, each participating institution will order the study agent(s) directly from supplier. A participating site may order the agent(s) only after the initial IRB approval for the site has been forwarded to the Coordinating Center.

13. STATISTICAL CONSIDERATIONS

13.1 Study Design

This will be an open label Phase II trial in participants with recurrent GBM. Cohort 1 and Cohort 2 will enroll concurrently. In Cohort 1, to ensure that adequate abemaciclib penetrates into the tumors and inhibits cellular proliferation, 15 participants with recurrent GBM who require reoperation will be treated with abemaciclib prior to surgery. After recovery from surgery, participants will receive abemaciclib until disease progression or the development of unacceptable toxicities. In Cohort 2, participants will receive abemaciclib without undergoing prior surgery. The two cohorts will be analyzed separately.

In Cohort 1 we will attempt to characterize the pharmacokinetic (PK) uptake of abemaciclib in brain. A single-time point brain-to-plasma ratio will be calculated for each participant with a paired plasma and brain sample, followed by a descriptive statistical analysis (mean, SD, CV% or median (range)). In addition, both a naive pool strategy of all brain samples as well as a non-linear mixed effect approach will be explored in an attempt to provide a better estimate of time-course of brain uptake, the total brain exposure over a dosing interval (AUC0-24) and the brain-plasma tissue partitioning coefficient (Kpt).

Cohort 1 will also assess for pharmacodynamic (PD) evidence of target inhibition in brain tissue. We will evaluate tumor tissue after treatment with abemaciclib for reduced RB1 signaling,

cellular proliferation, and increased cell death by immunohistochemistry for pRB1, Ki67, and cleaved caspase 3. The IHC effects will be evaluated by pathologist manual scoring of each marker as well as morphometric techniques to determine change relative to pre-abemaciclib biopsy which will also be stained. These results will be compared to a group of 15 patient samples who received treatment only with standard of care TMZ and RT. Results of the two cohorts will be compared statistically to determine whether significant changes are noted.

The primary goal of Cohort 2 is to determine the therapeutic efficacy of abemaciclib as measured by PFS6. Treatment duration will be measured in 4-week cycles. Participants will remain on treatment until tumor progression, as long as there are no unacceptable toxicities. Responses will be assessed by clinical examinations every 4 weeks and MRI scans every 8 weeks.

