5.2 Cohort 1—Surgery Arm

In Cohort 1, 15-20 eligible participants who require reoperation will be treated with abemaciclib for 10-14 days prior to surgery. The last dose should be on the day of surgery and taken 1-3 hours prior to surgery and tumor removal. Since participants in cohort 1 are undergoing PK testing, accurately recording the time of study drug administration on day of surgery and recording the time of tumor removal are especially important and required.

In general, pre-operative, operative, and post-operative evaluations will consist of standard clinical practice. Required evaluations and research samples are detailed in Section 10.

After surgery on study, cohort 1 participants will come off study treatment and pursue standard cancer treatments as per the treating physician's discretion. Participants who enrolled on the surgical cohort before the surgical cohort was converted into a Phase 0, who have already started post-surgical abemaciclib dosing, and are benefitting from post-surgical abemaciclib treatment may remain on abemaciclib at the discretion of their treating physician and the approval of the overall PI, [name]. These patients should instead follow the Study Calendar intended for Cohort 2 (nonsurgical) patients and their post-surgical C1D1 will represent C1D1 on the Cohort 2 study calendar.

Following registration, Cohort 1 pre-surgical Day 1 subjects should be evaluated for eligibility to treat based upon dose modification criteria outlined in Table 6.3 and not General Eligibility Criteria outlined here in Protocol Section 3; General Eligibility Criteria outlined here in Protocol Section 3 need only be met during screening for trial.

The goal is to have 15 eligible patients with adequate tissue for assessment of the primary objectives for this cohort. If sufficient tissue is not obtained for a patient enrolled in this cohort, the patient should continue treatment as originally intended and the clinical results reported. However, additional patients will be added to the cohort for the purpose of meeting the objectives related to tissue analysis. A maximum of 20 patients may be enrolled in this cohort. If the number of patients required to be replaced exceeds 5 consideration will be given to stopping enrollment to this cohort based on lack of feasibility.

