13.4 Analysis of Secondary and Exploratory Endpoints

Response rate will be the proportion of participants with measurable disease who experience complete or partial radiographic response determined by the RANO Criteria (Wen et al., 2010). Progression free survival, PFS6, and overall survival will be calculated using standard statistical methods. Safety will be summarized using descriptive statistics. Participants in Cohort 2 will not be replaced for any reason. If a subject enrolled in Cohort 1 is found at the time of on-treatment re-resection to have only necrosis and not recurrent disease, then s/he may remain on treatment but should be replaced for evaluation of endpoints.

In Cohort 1 & 2 plasma, and Cohort 1 tumor tissue levels of abemaciclib will be determined by liquid chromatography coupled with tandem mass spectrometry. Descriptive details of steady-state trough plasma levels, CSF and tumor tissue concentrations and tumor tissue to plasma ratios will be provided.

Other pharmacodynamic studies including immunohistochemistry and quantitative IHC analysis will be performed as in Section 9.0. Effects of abemaciclib on tumor cell proliferation and tumor cell death will be measured using immunohistochemistry for pRB1, Ki-67 and Cleaved Caspase 3. In general the pharmacodynamic and neuro-imaging results will be summarized in a descriptive manner with comparison between pre- and post-treatment assay results when possible.

Beyond the assessment of "success", more detailed analyses of the biological correlate data are exploratory. The statistical analysis will depend on the amount and quality of the data obtained as well as the overall success of the treatment.

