APPENDIX F ABEMACICLIB DOSING INSTRUCTIONS & DRUG DIARY (Cohort 1 Pre-Surgery)

o be completed by study personnel:							
Patient ID #	_ Patient Initials:	Pre-Surgery Cycle Month & Year:	Abemaciclib Dose:	_mg, two times a day.			
	TAKE	pill(s) in the morning and	_ pill(s) in the evening.				

Abemaciclib Description:

• Your study drug (Abemaciclib) is supplied as 50 mg mixture beige tablet.

Abemaciclib Instructions - When and How:

- Take study drug (Abemaciclib) twice a day, once in the morning and once in the evening.
- Take the drugs at approximately the same time each morning and evening, so that you are taking the drugs 12 hours apart. Morning and evening doses should be taken as close to a 7AM & 7PM schedule as possible (7 in the morning, 7 at night, 7 the next morning, and so on).
- Take the pill(s) with a glass of water and swallow them whole; do not chew them or crush them. Abemaciclib can be taken with or without food.
- Do not skip any doses.
- If you forget to take your pills in the morning you can take your missed dose up to 6 hours after your normally scheduled time. If it has been more than 6 hours, skip the dose and take the next scheduled dose at the usual time in the evening (one dose only). Please call your study nurse or doctor to discuss missed doses.
- If you forget to take your pills in the evening, you can take your missed dose up to 6 hours after your normally scheduled time. If it has been more than 6 hours from the missed dose (i.e., less than 6 hours to your next scheduled dose), skip the dose and take the next scheduled dose at the next usual time (one dose only). Please call your study nurse or doctor to discuss missed doses.
- If you vomit your pills, write this down in your pill diary. Do not take a replacement dose. Take the next scheduled dose as usual (one dose only). Please call your study nurse or doctor to discuss vomited doses.
- On the day of surgery, you will be asked to take your morning dose at the hospital; therefore, please bring your pills with you. Do not take any further doses after surgery. Return any remaining pills to the study team.

Additional Instructions:

- You must avoid eating or drinking any foods with Seville oranges (like marmalade), grapefruit or foods or drink with grapefruit, and any exotic fruits during the entire treatment period.
- You should drink 8 to 10 glasses of clear liquids a day for the entire treatment period.

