- Keep your study drug in the original container(s) at room temperature. Keep study drug away from children, persons cannot read the label, and pets.
- Do not throw away empty bottles, and do not throw the study drug in the trash or flush into the toilet.
- Bring this diary, all pill bottles, and any unused pills to each clinic visit. Your Treatment Team will collect your diary, all pill bottles and any unused study drug, and you will be given a new pill diary at that time.
- Contact your study doctor or nurse if you are having any new or worsening side effects. Contact your study doctor or nurse as soon as possible if you are experiencing diarrhea.
- Do not begin any new medication, over-the-counter drug, or herbal preparation without first checking with your study doctor or nurse to determine if it is acceptable to take while on this study.

Day 1	Day 2	Day 3	Day 4	Day 5	Day 6	Day 7
Date:	Date:	Date:	Date:	Date:	Date:	Date:
A.M. DOSE	A.M. DOSE	A.M. DOSE	A.M. DOSE	A.M. DOSE	A.M. DOSE	A.M. DOSE
No. of pills:	No. of pills:	No. of pills:	No. of pills:	No. of pills:	No. of pills:	No. of pills:
Time:	Time:	Time:	Time:	Time:	_ Time:	Time:
P.M. DOSE	P.M. DOSE	P.M. DOSE	P.M. DOSE	P.M. DOSE	P.M. DOSE	P.M. DOSE
No. of pills:	No. of pills:	No. of pills:	No. of pills:	No. of pills:	No. of pills:	No. of pills:
Гіте:	Time:	Time:	Time:	Time:	Time:	Time:
Initials	 Initials		 Initials	Initials	 Initials	 Initials
Day 8	Day 9	Day 10	Day 11	Day 12	Day 13	Day 14
Date:	Date:	Date:	Date:	Date:	Date:	Date:
A.M. DOSE	A.M. DOSE	A.M. DOSE	A.M. DOSE	A.M. DOSE	A.M. DOSE	A.M. DOSE
No. of pills:	No. of pills:	No. of pills:	No. of pills:	No. of pills:	_ No. of pills:	No. of pills:
Гіте:		Time:	Time:	Time:	_ Time:	Time:
P.M. DOSE	P.M. DOSE	P.M. DOSE	P.M.DOSE	P.M. DOSE	P.M. DOSE	P.M. DOSE
No. of pills:	_ No. of pills:	No. of pills:	No. of pills:	No. of pills:	No. of pills:	No. of pills:
Time:	_ Time:	Time:	Time:	Time:	Time:	Time:
Initials						 Initials
Please stop takii	ng abemaciclib after on-stud	ly surgery until you are ex	valuated by the study tear	m. All unused study med	lication should be returne	ed to the study team.
	Participant/Guard	lian Signature:		Date:		
	To be completed by	y study personnel: # o	f 50 mg Bottles Returned:	# of 50 m	ng Pills Returned:	
	Compare with drug diary ent	ries made by participant or	guardian. If discrepancy	(in the # of bottles or the	# of pills returned), pleas	e reconcile:
	Study Perso	nnel Signature:		Date:		

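### Section 13.1 keeps Cohort 1 on abemaciclib after surgery while Sections 1.1, 2.4 and 5.2 take it off, and two further sentences do not say which patients they cover

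*Combined protocol and SAP*

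**What the plan says.** The statistical section, 13.1, describes Cohort 1 treatment without qualification: "After recovery from surgery, participants will receive abemaciclib until disease progression or the development of unacceptable toxicities."

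The treatment plan in 5.2 (third paragraph) reads: "After surgery on study, cohort 1 participants will come off study treatment and pursue standard cancer treatments as per the treating physician's discretion." Sections 1.1 and 2.4 agree. Table 10.1 enters none for abemaciclib after surgery, and Appendix F tells the patient: "Do not take any further doses after surgery."

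Section 5.2 has one explicit exception. It concerns "Participants who enrolled on the surgical cohort before the surgical cohort was converted into a Phase 0" who have already begun post-surgical dosing and are benefitting, subject to the treating physician's discretion and the overall PI's approval. For monitoring: "These patients should instead follow the Study Calendar intended for Cohort 2 (nonsurgical) patients."

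Two more sentences bear on the question without naming a population:
- 5.2, last paragraph, when too little tissue is obtained: "the patient should continue treatment as originally intended and the clinical results reported."
- 13.4, when re-resection shows only necrosis: "then s/he may remain on treatment but should be replaced for evaluation of endpoints."

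The footer of the Appendix F diary (garbled in the extracted text, fragment "surgery until you are ex") ties stopping to a later evaluation by the study team. Section 5.1 still provides for a new diary after surgery for Cohort 1 patients who continue, and the Appendix E diary is still titled for Cohort 1 after surgery as well as for Cohort 2.

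**The concern.** Whether a patient takes an investigational drug after surgery should have one answer, and the current text gives two. Section 2.4 says the Phase 0 part is not meant to treat the tumor. It reports limited benefit in Cohort 2: PFS6 of 9.37% and median PFS of 55 days. A Phase 0 patient continued on drug would come under 5.4.13, which excludes other anticancer therapy during study treatment, while 5.2 sends the same patient to standard treatment. Both cannot be followed.

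The calendar written for Cohort 1 assumes that dosing has ended, so it schedules nothing that would support continued dosing.

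The analysis is affected too. Cohort 1 PFS and OS are timed from the first dose after surgery, and Section 9.2 plans to correlate immunologic markers from this cohort with those outcomes. The Cohort 1 primary endpoint, drug concentration in tumor, is not at stake, because the tissue is taken at surgery.

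**Working it through.** The point rests on no sample-size or power figure. The check sets the passages side by side.

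**1. Is the conflict in current text?** Yes. Section 13.1 and the third paragraph of 5.2 are both operative text, and neither is part of an amendment log. One says Cohort 1 will receive drug after recovery; the other says it comes off.

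**2. Does the 5.2 exception resolve it?** No. Apart from the required approvals, it has three conditions: enrolled before conversion, post-surgical dosing already started, and benefitting. Section 13.1 carries none of them and speaks of Cohort 1 participants generally.

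**3. What do the two unqualified sentences mean for a Phase 0 patient?**
- 5.2, insufficient tissue. Tissue yield is known only at surgery, so the sentence must concern what follows. For a pre-conversion patient the original intention was further drug. For a Phase 0 patient it was to stop. The wording fits either.
- 13.4, necrosis only. The sentence is permissive, and to remain on treatment presupposes being on it. It may have been meant for pre-conversion patients, but it does not say so.

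**4. What would apply if a Phase 0 patient were continued?** The Cohort 2 calendar is assigned only to the excepted group, so Table 10.1 governs.
- Hematology and chemistry: screening, Day 1 and Day 8; 0 after surgery.
- Vital signs, neurologic and physical examination, MRI: screening only; 0 after surgery.
- Footnote e: no protocol-specific assessment is required after surgery.
- Cohort 2 patients on the same drug (Table 10.2): laboratory tests at Cycle 1 Day 1, Cycle 1 Day 15 and Day 1 of each later cycle, with MRI at every odd cycle.

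Table 6.3 adjusts dosing on transaminases, creatinine, hemoglobin, neutrophils and platelets, and 13.1 would stop drug at progression. Both need laboratory tests or imaging that Table 10.1 does not schedule.

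**5. What safeguards remain?** Adverse events and concomitant medications are collected to 30 days after the last dose (Table 10.1, footnote l). A 30-day contact includes KPS (footnote f). Events causing a delay or reduction are followed at least weekly (6.2.3), and interruptions or discontinuations are followed under 6.2.10.

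**6. How many patients?** Section 5.2 aims for 15 patients with adequate tissue and allows 20 at most, so planned replacements are 20 − 15 = 5. That covers the whole of Cohort 1, pre-conversion patients included. Section 2.4 says only the remaining slots became Phase 0 and does not say how many. Read literally, 13.1 reaches every Phase 0 patient, a number that is not given.

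**7. Time origin.** Section 11.5 starts Cohort 1 PFS and OS at the first post-surgery treatment. Section 13.5 does the same and also requires a post-surgery dose for inclusion in the other efficacy analyses. A Phase 0 patient handled under 5.2 has no such dose, hence no start date and no place in those analyses.

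**The case against.** The strongest reply is that the documents a site works from mostly agree. The objectives, the rationale, the main rule in 5.2, the calendar and the diary bullet all end drug at surgery. The contrary sentence sits in a statistical paragraph that still calls the trial Phase II and reads like design text not updated at the conversion. Harm would require a site to follow it over the treatment plan. That makes the consequence conditional. It does not remove the conflict, since nothing says which section prevails.

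Several stronger readings are tempting and are not supported:
- *Section 5.2 gives opposite orders, so adequate tissue means off drug and inadequate tissue means on.* The phrase in "the patient should continue treatment as originally intended and the clinical results reported" can mean the Phase 0 course, in which case tissue yield changes nothing. The sentence is ambiguous, as is the one in 13.4.
- *Appendix F tells the patient two opposite things.* Both sentences tell the patient to stop, and both places ask for unused drug to be returned. The footer is looser because it leaves open what follows the evaluation, but it does not tell anyone to resume.
- *A continued patient would be unmonitored.* The safeguards in step 5 would remain. What is missing is scheduled visits, laboratory tests and imaging after surgery.
- *Five Phase 0 patients are affected.* The allowance of 5 is for the whole cohort, and the Phase 0 share is unknown.

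**Conclusion.** The concern holds. Section 13.1 contradicts 1.1, 2.4, the third paragraph of 5.2, Table 10.1 and the Appendix F bullet on post-surgery dosing. The insufficient-tissue sentence in 5.2 and the necrosis sentence in 13.4 lack a stated population and can be read either way.

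The consequence for patients depends on a site following 13.1, or the continue-treatment reading of the other two sentences. The documents do not show that any patient has been treated that way. The effect on the analysis needs no such step: under 5.2, the time origin in 11.5 and 13.5 is undefined for Phase 0 patients.

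The conflict should be corrected despite the unknown number affected, because it decides whether a patient receives investigational drug and may receive other therapy. This conclusion takes no position on which post-surgery rule is clinically right.

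**What to change.** Reconcile 1.1, 2.4, 5.1 (post-surgery diary), 5.2, 11.5, 13.1, 13.4, 13.5, Table 10.1 and Appendices E and F in one amendment:
- State one post-surgery rule for each type of Cohort 1 patient: enrolled before conversion, Phase 0, insufficient tissue, necrosis only.
- Say which patients each continue-treatment sentence covers.
- Tie any post-surgery dosing that remains allowed to a named study calendar.
- Align the Cohort 1 time origin, and the post-surgery dose condition in 13.5, with the reconciled rule.
- Use a single consistent sentence in the patient diary.

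The choice of clinical rule belongs to the sponsor. The cost is a wording amendment and a revised diary page, with no added patients. No procedures are added unless the sponsor keeps post-surgery dosing for patients who now have no calendar for it.
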